	Screening		Blinded, Placebo- Controlled Treatment Part A										Open-label Part B					Follow-up Part Ca
Visit	1	1a	2	3	4	5	6	7	8	9	10	11	12	13	14	15	ET	801
Week of Treatment			Base- line 0	1	2	4	8	12	14	16	20	24	28	32	40	52	Any week	
Days from Visit 2	-42 to -3 days		0	7 ± 2 days	14 ± 2 days	28 ± 2 days	56 ± 3 days	84 ± 3 days	98 ± 3 days	112 ± 3 days	140 ± 3 days	168 ± 3 days	196 ± 3 days	224 ± 5 days	280 ± 5 days	365 ± 5 days	Any day	28 ± 5 days after last dose
Physician global assessment of disease activity			X	X	X	X	X	X	X	X	X	X	X	X	X	X	X	X
Hand and foot x-rays ⁱ	X ⁱ									X		X				X	X ⁱ	
HAQ-DI			X	X	X	X	X	X	X	X	X	X	X	X	X	X	X	X
Morning joint stiffness - diary			X ^k															
Morning joint stiffness - tablet ^l			X	X	X	X	X	X	X	X	X	X	X	X	X	X	X	X
FACIT-F			X			X	X	X		X	X	X	X	X	X	X	X	X
EQ-5D-5L			X			X	X	X		X	X	X	X	X	X	X	X	X
Worst tiredness NRS-diary			X ^k															
Worst tiredness NRS-tablet ^l			X	X	X	X	X	X	X	X	X	X	X	X	X	X	X	X
WPAI-RA			X		X	X	X	X		X	X	X	X	X	X	X	X	X
Worst joint pain NRS-diary			X ^k															
Worst joint pain NRS-tablet ^l			X	X	X	X	X	X	X	X	X	X	X	X	X	X	X	X
QIDS-SR16			X					X				X				X	X	X
Healthcare resource use			X			X	X	X		X	X	X	X	X	X	X	X	X
Laboratory tests																		
TSH	X																	
HIV	X																	
Hepatitis C antibody testing	X																	
Hepatitis B testing (HBsAg, HBcAb, HBsAb)	X																	

Visit	Screening		Blinded, Placebo- Controlled Treatment Part A										Open-label Part B				ET	Follow-up Part Ca
	1	1a	2	3	4	5	6	7	8	9	10	11	12	13	14	15		
Week of Treatment			Base-line 0	1	2	4	8	12	14	16	20	24	28	32	40	52	Any week	
Days from Visit 2	-42 to -3 days		0	7 ± 2 days	14 ± 2 days	28 ± 2 days	56 ± 3 days	84 ± 3 days	98 ± 3 days	112 ± 3 days	140 ± 3 days	168 ± 3 days	196 ± 3 days	224 ± 5 days	280 ± 5 days	365 ± 5 days	Any day	28 ± 5 days after last dose
Serum pregnancy test ^m	X		X															
Urine pregnancy test ^m			X	X	X	X	X	X	X	X	X	X	X	X	X	X	X	X
FSH ⁿ	X																	
Clinical chemistry ^o	X		X	X	X	X	X	X	X	X	X	X	X	X	X	X	X	X
Lipid panel ^p			X					X				X				X		
Lipid NMR ^q			X					X										
Hematology	X		X	X	X	X	X	X	X	X	X	X	X	X	X	X	X	X
HBV DNA ^r								X				X		X	X	X	X ^s	
Iron studies (iron, TIBC, and ferritin)	X		X					X				X				X		
Urinalysis	X		X					X				X		X		X	X	
Rheumatoid factor	X		X					X				X				X	X	
hsCRP	X		X	X	X	X	X	X	X	X	X	X	X	X	X	X	X	X
Erythrocyte sedimentation rate ^t	X		X	X	X	X	X	X	X	X	X	X	X	X	X	X	X	X
Anti-CCP	X		X					X				X				X	X	

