- a Assayed/calculated by a sponsor-designated laboratory.
- b Unscheduled blood chemistry (including CPK), hematology, and urinalysis panels may be performed at the discretion of the investigator. If tests are done to evaluate laboratory results to resume study drug, samples must be assayed centrally.
- c Estimated glomerular filtration rate for serum creatinine calculated by the central laboratory using the Modification of Diet in Renal Disease isotope dilution mass spectrometry traceable method.
- d The calculated creatinine clearance will be determined by the central laboratory each time a serum creatinine sample is collected using the Cockcroft-Gault equation: Men: $([140 - \text{age}] \times [\text{weight in kg}]) / (72 \times [\text{serum creatinine in mg/dL}])$ or $([140 - \text{age}] \times [\text{weight in kg}]) / (0.814 \times [\text{serum creatinine in } \mu\text{mol/L}])$. Women: $(\text{above formula}) \times 0.85$.
- e Fasting laboratory values for glucose and lipids will be required at baseline, Week 12, Week 24, and Week 52. If a patient attends these visits in a nonfasting state, this will not be considered a protocol violation. These tests may be performed nonfasting at all other visits.
- f For all women of childbearing potential, a serum pregnancy test (central laboratory) will be performed at Visit 1 and both urine (local laboratory) and serum pregnancy (central laboratory) tests will be performed at Visit 2 to determine study eligibility. Urine pregnancy tests (local laboratory) will also be performed at each subsequent study visit per study schedule.
- g To confirm postmenopausal status for women ≥ 40 and < 60 years of age, an FSH test will be performed. Nonchildbearing potential is defined as an FSH ≥ 40 mIU/mL and a cessation of menses for at least 12 months.
- h A positive hepatitis C antibody result will be confirmed with a positive hepatitis C virus result.
- i Microscopic examination of sediment will be performed only if abnormalities are noted on the routine urinalysis.
- j Test will be required at Visit 1 only to determine eligibility of patient for the study. In countries where the QuantiFERON-TB Gold or T-SPOT.TB test is available and, in the judgment of the investigator, medically preferred as an alternative to the PPD test for the evaluation of mycobacterium tuberculosis (MTB) infection, it may be used instead of the PPD test (positive tests excluded) and may be read locally.

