Treatment comparisons of continuous efficacy and health outcomes variables will be made using analysis of covariance (ANCOVA) with country, treatment group, baseline joint erosion status, and baseline value in the model. Type III sums of squares for the least-squares (LS) means will be used for the statistical comparison; the 95% CI will also be reported.

When a restricted maximum likelihood (REML)-based mixed model for repeated measures (MMRM) is used (as a sensitivity model for continuous secondary variables [see Section 6.11.2]), the model will include treatment, country, baseline joint erosion status (1-2 joint erosions plus seropositivity versus at least 3 joint erosions), visit, and treatment-by-visit-interaction as fixed categorical effects and baseline score and baseline score-by-visit-interaction as fixed continuous effects to estimate change from baseline across post-baseline visits. An unstructured covariance structure will be used to model the between- and within-patient errors. If this analysis fails to converge, other structures will be tested such as heterogeneous autoregressive [ARH(1)], heterogeneous compound symmetry (CSH), or heterogeneous Toeplitz (TOEPH). The variance-covariance structure that results in the smallest Akaike information criterion (AIC) will be used. The Kenward-Roger method will be used to estimate the denominator degrees of freedom. Type III sums of squares for the LS means will be used for the statistical comparison; the 95% CI will also be reported. Treatment group comparisons at Week 12 and all other visits will be tested.

The Fisher exact test will be used to perform treatment comparisons for AEs, discontinuations, and other categorical safety data among treatment groups. Change from baseline in continuous vital signs, physical characteristics, and other continuous safety variables, including laboratory variables, will be analyzed using an ANCOVA model with explanatory terms for treatment and the baseline value as a covariate. Type III sums of squares will be used. The significance of within-treatment group changes from baseline will be evaluated by testing whether the treatment group LS mean changes from baseline are different from zero using a t-statistic; the standard error for the LS mean change will also be displayed. Differences in LS means as compared to placebo will be displayed with the associated p-value and a 95% CI of the LS mean difference.

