6.14.3. Laboratory Measurements

All laboratory tests will be presented using Système International of units (SI units). For topics of safety in special groups and circumstances, laboratory test units will be specified for each analysis.

Lilly large clinical trial population based reference limits (Lilly-defined; LCTPB) will be used to define the low and high limits since it is generally desirable for limits used for analyses to have greater specificity (identify fewer false positive cases) than reference limits used for individual patient management. For the hepatic laboratory assessments (ALT, AST, total bilirubin, and alkaline phosphatase [ALP]), central laboratory reference ranges (Quintiles) will be used and all results pertaining to these assessments will be included as a separate analysis to address the risk of liver injury as a special safety topic (see [Section 6.14.4.1](#)). Central laboratory reference ranges (Quintiles) will also be used to evaluate immunoglobulins (see [Section 6.14.3](#)).

The ratio of the low-density lipoprotein (LDL) cholesterol value to the high-density lipoprotein (HDL) cholesterol, referred to as the LDL/HDL ratio, will be derived for each patient at each visit where both values are simultaneously available. This lab parameter was not included in the standard lab processing for the Phase 3 RA studies and, as such, will not have valid reference

ranges for comparison of the ratio to a standard for characterization as treatment-emergent abnormal.

Change from baseline to last observation for laboratory tests will be summarized for patients who have both baseline and at least 1 postbaseline result. Baseline will be the last nonmissing observation in the baseline period prior to receiving the first dose of the study drug. The last nonmissing observation in the treatment period will be used for this analysis. Unscheduled measurements will be excluded.

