Change from the minimum value during the baseline period to the minimum value during the treatment period for selected laboratory tests will be summarized for patients who have both baseline and at least 1 post-baseline result. Baseline will be the minimum of non-missing observations in the baseline period. The minimum value in the treatment period will be used for this analysis. Similarly, change from the maximum value during the baseline period to the maximum value during the treatment period for selected laboratory tests will be summarized for patients who have both baseline and at least 1 post-baseline result. Baseline will be the maximum of non-missing observations in the baseline period. The maximum value in the treatment period will be used for this analysis. Original-scale data will be analyzed. Scheduled and unscheduled measurements will be included.

The change from baseline in laboratory assessments, using each of the 3 approaches above, will be summarized using standard descriptive statistics.

In addition, laboratory assessments will be summarized with descriptive statistics (n, mean, SD, minimum, median, and maximum) by time point. Summaries will be provided for baseline and for each postbaseline visit by treatment group, including change from baseline and percent change from baseline. These summaries will be based on patients who have both baseline and at least 1 postbaseline assessment.

The number and percent of patients with treatment-emergent abnormal, high, or low laboratory results at any time will be summarized by treatment group.

- A treatment-emergent **abnormal** result is defined as a change from normal at all baseline visits to abnormal at any time during the treatment period.
- A treatment-emergent **high** result is defined as a change from a value less than or equal to the high limit at all baseline visits to a value greater than the high limit at any time during the treatment period.
- A treatment-emergent **low** result is defined as a change from a value greater than or equal to the low limit at all baseline visits to a value less than the low limit at any time during the treatment period.

Scheduled and unscheduled measurements will be included in analysis of treatment-emergent abnormal, high, or low laboratory results. Differences between treatments (when appropriate) in incidence of treatment-emergent abnormal, high, or low laboratory results will be assessed using the Fisher exact test.

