Treatment-emergent elevated total cholesterol will be characterized as movement from categories 'Desirable' or 'Borderline High' to category 'High' considering patients who are at risk for the abnormality, that is, not 'High' based on the maximum baseline total cholesterol category. Treatment-emergent elevated LDL cholesterol will be characterized as movement from categories 'Optimal,' 'Near optimal,' or 'Borderline high' to categories 'High' or 'Very high' considering patients who are at risk for the abnormality, that is, neither 'High' nor 'Very high' based on the maximum baseline LDL cholesterol category. Treatment-emergent decreased HDL cholesterol will be characterized as movement from categories 'High' or 'Normal' to category 'Low' considering patients who are at risk for the abnormality, that is, not 'Low' based on the minimum baseline HDL cholesterol category. Treatment-emergent elevated triglycerides will be characterized as movement from categories 'Normal' or 'Borderline high' to categories 'High' or 'Very high' considering patients who are at risk for the abnormality, that is, neither 'High' nor 'Very high' based on the maximum baseline triglycerides category. Scheduled and unscheduled measurements will be included.

Shift tables will show the number and percent of patients with measurement in each category based on baseline to maximum or minimum category during the treatment period, with baseline depicted by the most extreme category during the baseline period. With each shift table, a shift table summary will display the number and percentage of patients with maximum or minimum postbaseline results overall and by treatment group within the following categories:

- Decreased; postbaseline category < baseline category,
- Increased; postbaseline category > baseline category,
- Same; postbaseline category = baseline category.

Treatment differences for the shift table summary categorizations may be assessed with the Likelihood Ratio Chi-Square test, using the exact version of this test whenever at least 1 cell has an expected cell count <5. Furthermore, a summary of category increases by each maximum category will be provided.

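### The SAP has no fasting rule for glucose, although nonfasting draws are allowed at 10 of the 13 scheduled postbaseline treatment visits

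*SAP*

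**What the plan says.** Protocol Attachment 2 lists glucose under clinical chemistry, with a footnote on fasting: "Fasting laboratory values for glucose and lipids will be required at baseline, Week 12, Week 24, and Week 52". The footnote adds "These tests may be performed nonfasting at all other visits". It also tolerates lapses at the fasting visits: "If a patient attends these visits in a nonfasting state, this will not be considered a protocol violation". In the Attachment 1 schedule the row "Clinical chemistry" is marked at screening, at baseline, at all 13 postbaseline treatment visits, at early termination and at follow-up.

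The SAP does not carry the fasting distinction forward.

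- **By visit (6.14.3):** "Summaries will be provided for baseline and for each postbaseline visit by treatment group, including change from baseline and percent change from baseline".
- **Change to last observation (6.14.3):** baseline is the last predose value, expected at Week 0. On the other side, "The last nonmissing observation in the treatment period will be used for this analysis".
- **Treatment-emergent high (6.14.3):** any treatment-period value counts, scheduled or unscheduled, and the arms are compared with the Fisher exact test.
- **Testing (6.1):** changes in laboratory variables go into ANCOVA, and the plan also tests "whether the treatment group LS mean changes from baseline are different from zero using a t-statistic".
- **Carry-forward (6.3.1, Table 6-1):** laboratory values use mLOCF, so a rescued patient's value at or before rescue is carried on to Week 24.
- **Early termination (6.1):** these data are mapped to the patient's next scheduled visit.

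**The concern.** By requiring fasting at four visits, the protocol treats fasting state as relevant to glucose. The SAP then analyses fasting-required and other draws as one measure. A rise from Week 0 to Week 4, for example, could reflect breakfast and not drug, and the plan attaches a within-group p-value to it. An any-time high rate that mixes both kinds of draw can be inflated in both arms.

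The between-arm comparison can also be affected. Part A safety comparisons use data only up to rescue. A patient rescued at Week 16 or Week 20 leaves a last value from a visit where fasting was not required, whereas a Week 24 completer leaves one from a fasting-required visit. If rescue is more common on placebo, the placebo mean is pushed up and a true rise on baricitinib is partly masked.

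**Working it through.** The documents give no figure on this point to reproduce.

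**Step 1. Visit count (Attachments 1 and 2).** Scheduled postbaseline treatment visits with chemistry are Weeks 1, 2, 4, 8, 12, 14, 16, 20, 24, 28, 32, 40 and 52, which is 13. Fasting is required at Weeks 12, 24 and 52, which is 3.

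| Period | Visits | Fasting required | Nonfasting allowed |
|---|---|---|---|
| Through Week 12 | 5 | 1 | 4 |
| Through Week 24 (Part A) | 9 | 2 | 7 |
| Through Week 52 | 13 | 3 | 10 |

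Early-termination and follow-up draws, also without a fasting requirement, are not counted here.

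**Step 2. Within-group test with no drug effect.** t = shift / (SD / √n), with n = 144 per arm from the sample size section. The mean fed shift (0.3 to 1.0 mmol/L, averaged over all patients at the visit) and the SD of change (1.0 to 1.5 mmol/L) are assumptions.

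- Low end: 0.3 / (1.5 / 12) = 2.4.
- High end: 1.0 / (1.0 / 12) = 12.

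Both exceed the two-sided 0.05 threshold.

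**Step 3. Any-time highs through Week 24 with no drug effect.** For a patient not rescued, P = 1 − (1 − qf)² × (1 − qn)⁷. Here qf and qn are assumed per-visit rates of a high value at fasting and nonfasting visits, and visits are treated as independent.

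- qf = 1%, qn = 5%: 1 − 0.99² × 0.95⁷ = 31.6%, against 1 − 0.99⁹ = 8.6% if all nine draws were fasting.
- qf = 2%, qn = 10%: 1 − 0.98² × 0.90⁷ = 54.1%, against 1 − 0.98⁹ = 16.6%.

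The inflation is the same in both arms when rescue is equal.

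**Step 4. Week 24 last-observation or mLOCF mean.** Placebo minus baricitinib = fed shift × (placebo rescue rate − baricitinib rescue rate). The documents give no rescue rates, so the ones used are assumptions.

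- 18% versus 7%, shift 0.3: 0.11 × 0.3 = 0.03 mmol/L.
- 46% versus 22%, shift 1.0: 0.24 × 1.0 = 0.24 mmol/L.
- Equal rescue: 0.

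This source is absent through Week 12, because rescue starts at Week 16.

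**Step 5. Any-time highs with unequal rescue.** A patient censored at Week 16 has one fasting and six other draws, so P = 1 − (1 − qf)(1 − qn)⁶. With assumed rescue of 5 to 10% on baricitinib and 20 to 40% on placebo, and qf/qn from 1%/3% to 2%/10%, baricitinib is higher by 0.5 to 1.8 percentage points. In the most extreme case the Fisher test rejects 4.8% of the time, against 3.9% with equal rates.

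**The case against.** A reader might infer that the plan biases the arm comparison by its design alone. The documents do not support that. Both arms follow the same visit and fasting schedule, nonfasting attendance is permitted and not prescribed, and an arm difference needs unequal rescue or dropout. Where it arises, the effect on any-time highs is small and opposite in direction to the effect on the last-observation mean. Early-termination draws could move the result either way.

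A reader might also take the by-visit sentence in SAP 6.14.3 as pooling visits. It does not: it summarises each visit separately. Mixing occurs in the any-time analysis, and would occur in the minimum and maximum analyses if glucose is one of the selected tests, which the SAP does not say. Those analyses do not have a purely fasting baseline either, because the baseline period starts at Visit 1, where nonfasting is allowed.

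Extending the point to lipids is tempting, since SAP 6.14.4.3 says "Scheduled and unscheduled measurements will be included". But the lipid panel is scheduled only at baseline and Weeks 12, 24 and 52. The provision for unscheduled tests in Attachment 2 names chemistry, hematology and urinalysis panels, so no lipid change is warranted.

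Finally, glucose is not an adverse event of special interest, and the fed shifts, SDs and rescue rates above are assumed. These points limit the concern's size and importance. They do not supply the missing rule: a baseline expected to be fasting is still compared, with p-values, against values that may not be.

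**Conclusion.** The concern holds as a gap in the SAP's handling of glucose. The visit counts and the absence of a fasting rule are matters of record. The consequences are conditional. If patients attend fed, within-group changes at up to 10 of 13 visits, and any-time highs, can rise in both arms without a drug effect. If rescue is also more frequent on placebo, the Week 24 last-observation and mLOCF placebo mean can be raised by roughly 0.03 to 0.24 mmol/L relative to baricitinib, under assumed shifts of 0.3 to 1.0 mmol/L and rescue differences of 11 to 24 percentage points. No primary or secondary efficacy conclusion is affected. It is a low-cost correction to one safety analyte.

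**What to change.** In SAP 6.14.3, with a cross-reference from 6.1 and 6.3.1:

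- Base the tested glucose change-from-baseline, last-observation and mLOCF analyses on Weeks 0, 12, 24 and 52, and carry forward only values from those visits.
- Do not treat early-termination draws mapped to those visits as fasting.
- Report treatment-emergent high glucose in two parts, one for the fasting-required visits and one for all other draws, including unscheduled ones, so that no surveillance data are lost.
- Summarise glucose at the other visits descriptively, labelled as not requiring fasting.

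This needs SAP wording and a visit filter on data already collected, and is best settled before unblinding. Three postbaseline time points remain in the tested analysis, two of them in Part A. Some nonfasting values will remain, because nonfasting attendance at the fasting visits is not a violation.

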6.14.4. Safety in Special Groups and Circumstances, including Adverse Events of Special Interest

In addition to general safety parameters, safety information on specific topics of special interest will be presented. Topics will be identified by laboratory results, standardized MedDRA queries (SMQs), Lilly-defined MedDRA PT listings, or a combination of these methods. The primary focus of analyses will be on laboratory test values, where applicable, with a secondary focus on reported AEs related to laboratory values. Additional special safety topics may be added as warranted. The topics outlined in this section include the protocol-specified AESI:

- severe or potential opportunistic infections
- myelosuppressive events of anemia, leukopenia, neutropenia, lymphopenia, and thrombocytopenia
- thrombocytosis
- elevations in ALT or AST ($>3 \times$ ULN) with total bilirubin ($>2 \times$ ULN).

In general, for topics regarding safety in special groups and circumstances, patient listings, where applicable, will be provided when needed to allow medical review of the time course of cases/events, related parameters, patient demographics, study drug treatment, and meaningful concomitant medication use. In addition to the safety topics for which provision or review of patient data is specified, these will be provided when summary data are insufficient to permit adequate understanding of the safety topic.

6.14.4.1. Abnormal Hepatic Tests

Analyses for abnormal hepatic tests involve 5 lab analytes: ALT, AST, total bilirubin, ALP, and albumin. Analyses for change from baseline to last observation, change from the minimum value during the baseline period to the minimum value during the treatment period, change from the maximum value during the baseline period to the maximum value during the treatment period, and treatment-emergent high or low laboratory results at any time are described in Section 6.14.3. This section describes additional analyses for the topic. Recall also that central laboratory reference ranges (Quintiles) will be used for some hepatic laboratory assessments (ALT, AST, total bilirubin, and ALP).

The number and percent of patients with the following elevations in hepatic laboratory tests at any time will be summarized between treatment groups:

- The percentages of patients with an ALT measurement $\geq 3 \times$, $5 \times$, and $10 \times$ the central laboratory ULN during the treatment period will be summarized for all patients with a postbaseline value and for subsets based on various levels of baseline.

- The analysis of $3 \times \text{ULN}$ will contain 4 subsets: patients whose nonmissing maximum baseline value is $\leq 1 \times \text{ULN}$, patients whose maximum baseline is $>1 \times \text{ULN}$ but $<3 \times \text{ULN}$, patients whose maximum baseline value is $\geq 3 \times \text{ULN}$, and patients whose baseline values are missing.
- The analysis of $5 \times \text{ULN}$ will contain 5 subsets: patients whose nonmissing maximum baseline value is $\leq 1 \times \text{ULN}$, patients whose maximum baseline is $>1 \times \text{ULN}$ but $<3 \times \text{ULN}$, patients whose maximum baseline is $\geq 3 \times \text{ULN}$ but $<5 \times \text{ULN}$, patients whose maximum baseline value is $\geq 5 \times \text{ULN}$, and patients whose baseline values are missing.
- The analysis of $10 \times \text{ULN}$ will contain 6 subsets: patients whose nonmissing maximum baseline value is $\leq 1 \times \text{ULN}$, patients whose maximum baseline is $>1 \times \text{ULN}$ but $<3 \times \text{ULN}$, patients whose maximum baseline is $\geq 3 \times \text{ULN}$ but $<5 \times \text{ULN}$, patients whose maximum baseline is $\geq 5 \times \text{ULN}$ but $<10 \times \text{ULN}$, patients whose maximum baseline value is $\geq 10 \times \text{ULN}$, and patients whose baseline values are missing.

- The percentages of patients with an AST measurement $\geq 3 \times$, $5 \times$, and $10 \times$ the central laboratory ULN during the treatment period will be summarized for all patients with a postbaseline value and for subsets based on various levels of baseline. Analyses will be constructed as described above for ALT.
- The percentages of patients with a total bilirubin measurement $\geq 2 \times$ the central laboratory ULN during the treatment period will be summarized for all patients with a postbaseline value and subset into 4 subsets: patients whose nonmissing maximum baseline value is $\leq 1 \times \text{ULN}$, patients whose maximum baseline is $>1 \times \text{ULN}$ but $<2 \times \text{ULN}$, patients whose maximum baseline value is $\geq 2 \times \text{ULN}$, and patients whose baseline values are missing.
- The percentages of patients with an ALP measurement $\geq 1.5 \times$ the central laboratory ULN during the treatment period will be summarized for all patients with a postbaseline value and subset into 4 subsets: patients whose nonmissing maximum baseline value is $\leq 1 \times \text{ULN}$, patients whose maximum baseline is $>1 \times \text{ULN}$ but $<1.5 \times \text{ULN}$, patients whose maximum baseline value is $\geq 1.5 \times \text{ULN}$, and patients whose baseline values are missing.

A by-patient listing will be provided for an ALT or AST measurement $\geq 3 \times \text{ULN}$, or with an ALP measurement $\geq 1.5 \times \text{ULN}$, or with a total bilirubin measurement $\geq 2 \times \text{ULN}$. The listing will include relevant demographic, study drug, concomitant therapy, AEs, and laboratory data.

To further evaluate potential hepatotoxicity, an Evaluation of Drug-Induced Serious Hepatotoxicity (eDISH) plot will be created. Each patient with at least 1 post-baseline ALT and total bilirubin contributes 1 point to the plot. The points correspond to maximum total bilirubin and maximum ALT, even if not obtained from the same blood draw.

Criteria for AE grading from the Common Terminology Criteria for Adverse Events (CTCAE) will be applied for the hepatic laboratory tests AST, ALT, ALP, total bilirubin, and albumin ([Table 6-3](#)). These CTCAE grading schemes are consistent with both Version 3.0 and Version

4.03 of the CTCAE guidelines. When deriving CTCAE grades for laboratory analytes with absolute criteria for grading, such as albumin, an adjustment to the CTCAE-defined approach will be made. The use of a lower limit of normal/upper limit of normal (LLN/ULN) from appropriate reference ranges will be replaced with a simpler approach that uses a single value. This adjustment to the CTCAE grading criteria overcomes the irresolute derivation of the grade that can occur when some demographically-specific LLN/ULN values (from either the Lilly LCTPB or the Quintiles reference ranges) overlap with the CTCAE-defined value that separates normal (Grade 0) and Grade 1.

Table 6-3. Common Terminology Criteria for Adverse Events Related to Hepatic Tests

Laboratory Test	Laboratory Units	Grade	Criteria
Albumin	SI	0 (normal)	$\geq 35 \text{ g/L}$
		1	$<35 \text{ g/L}$ and $\geq 30 \text{ g/L}$
		2	$<30 \text{ g/L}$ and $\geq 20 \text{ g/L}$
		3	$<20 \text{ g/L}$
ALT	SI	0 (normal)	$\leq \text{ULN}$
		1	$>\text{ULN}$ and $\leq 2.5 \times \text{ULN}$
		2	$>2.5 \times \text{ULN}$ and $\leq 5 \times \text{ULN}$
		3	$>5 \times \text{ULN}$ and $\leq 20 \times \text{ULN}$
		4	$>20 \times \text{ULN}$
AST	SI	0 (normal)	$\leq \text{ULN}$
		1	$>\text{ULN}$ and $\leq 2.5 \times \text{ULN}$
		2	$>2.5 \times \text{ULN}$ and $\leq 5 \times \text{ULN}$
		3	$>5 \times \text{ULN}$ and $\leq 20 \times \text{ULN}$
		4	$>20 \times \text{ULN}$
ALP	SI	0 (normal)	$\leq \text{ULN}$
		1	$>\text{ULN}$ and $\leq 5 \times \text{ULN}$
		2	$>5 \times \text{ULN}$ and $\leq 20 \times \text{ULN}$
		3	$>20 \times \text{ULN}$
		4	$>20 \times \text{ULN}$
Total bilirubin	SI	0 (normal)	$\leq \text{ULN}$
		1	$>\text{ULN}$ and $\leq 1.5 \times \text{ULN}$
		2	$>1.5 \times \text{ULN}$ and $\leq 3 \times \text{ULN}$
		3	$>3 \times \text{ULN}$ and $\leq 10 \times \text{ULN}$
		4	$>10 \times \text{ULN}$

Abbreviations: ALP = alkaline phosphatase; ALT = alanine transaminase; AST = aspartate aminotransferase; ULN = upper limit of normal.

Treatment-emergent laboratory abnormalities related to hepatic abnormalities occurring at any time during the treatment period will be tabulated. Treatment-emergence will be characterized using 2 criteria (as appropriate to the grading scheme):

- any increase in post-baseline CTCAE grade from worst baseline grade
- an increase from worst baseline less than Grade 3 to Grade 3 or Grade 4 at worst post-baseline

Treatment comparisons will be made using the Fisher exact test as appropriate. Scheduled and unscheduled measurements will be included.

Treatment-emergent laboratory abnormalities related to hepatic abnormalities shift tables of baseline to maximum during the treatment period will be tabulated. Shift tables will show the number and percent of patients with measurement in each category based on baseline to maximum CTCAE grade during the treatment period (Part A and B), with baseline depicted by the most extreme grade during the baseline period. A shift table summary displaying the number and percent of patients with maximum postbaseline results will be presented overall and by treatment group within the following categories:

- Decreased; post-baseline category < baseline category,
- Increased; post-baseline category > baseline category,
- Same; post-baseline category = baseline category.

The number and percent of patients with treatment-emergent hepatic laboratory abnormalities based on CTCAE grades will be summarized in terms of shift tables descriptively comparing baseline to maximum and last post-treatment follow-up grade and follow-up baseline to maximum and last post-treatment follow-up grade by treatment group. A shift table summary for each analysis will also be included. Furthermore, a summary of grade increases by each maximum and last grade will be provided.

First shift table summary:

- Decreased; maximum post-treatment follow-up category < baseline category
- Increased; maximum post-treatment follow-up category > baseline category
- Same; maximum post-treatment follow-up category = baseline category

Second shift table summary:

- Decreased; maximum post-treatment follow-up category < follow-up baseline category
- Increased; maximum post-treatment follow-up category > follow-up baseline category
- Same; maximum post-treatment follow-up category = follow-up baseline category

Third shift table summary:

- Decreased; last post-treatment follow-up category < baseline category
- Increased; last post-treatment follow-up category > baseline category
- Same; last post-treatment follow-up category = baseline category

Fourth shift table summary:

- Decreased; last post-treatment follow-up category < follow-up baseline category
- Increased; last post-treatment follow-up category > follow-up baseline category
- Same; last post-treatment follow-up category = follow-up baseline category

